4.6.2 Safety Variables

4.6.2.1 Adverse Drug Reactions: The most serious adverse reaction reported in subjects in clinical studies who received Berinert® was an increase in the severity of pain associated with hereditary angioedema. In a placebo controlled clinical study, the incidence of adverse events occurring in more than 4% of subjects (n = 43) receiving Berinert® up to 72 hours after infusion was nausea (7%), headache (7%), abdominal pain (7%), dysqeusia (4.7%), vomiting (2.3%), pain (2.3%), and muscle spasms (2.3%). Adverse reactions can persist 7-9 days after infusion and have been reported to be abdominal pain (6.5%), diarrhea (4.6%), nausea (6.5%), vomiting (4.6%), headache (11.1%), hereditary angioedema recurrence (11.1%), muscle spasm (5.6%), and pain (5.6%). Subjects were tested at baseline and after 3 months for exposure to parvovirus B19, HBV, HCV, and HIV-1 and HIV-2. No subject who underwent testing evidenced seroconversion or treatment-emergent positive polymerase chain reaction testing for the above pathogens. Post-marketing reports from Europe since 1979 in patients receiving Berinert®

for treatment of HAE include hypersensitivity/anaphylactic reactions, a few suspected cases of viral transmission, including cases of acute hepatitis C, injection-site pain, injection-site redness, chills, and fever. See Novation Drug Monograph for Berinert® (Appendix B).

- 4.6.2.2 Assessment of Risk for Thrombotic Events with C1INH Administration: Patients with known risk factors for thrombotic events will be monitored for signs and symptoms of thrombosis, such as new onset swelling and pain in the limbs or abdomen, new onset chest pain, shortness of breath, loss of sensation or motor power, or altered consciousness, vision, or speech. To address the increased risk of TE, we will apply the Well's criteria for diagnosis of DVT (http://www.mdcalc.com/wells-criteria-for-dvt) (Wells, 2003,2006,2006). Patients will be assessed with each infusion for evidence of DVT or other TEs. Those receiving a high-risk score will have lower-extremity Doppler venous ultrasounds to rule-out the presence of DVTs. In addition, routine measurements of coagulation factors to evaluate DIC (D-Dimers, fibrinogen, PT, PTT) will be performed (See Appendix A).
- 4.6.2.3 Evidence of a Thrombotic Effect of C1INH Administration when Given in Supraphysiologic Dosages to Humans: The German Medical Profession's Drugs Committee (AkdÅ) reported on 13 cases of severe thrombus formation after Berinert® infusions Arzteblatt, 2000). These infusions were given to neonates undergoing cardiac surgery and doses of Berinert® were given at exceedingly high doses (~500U/kg) without control studies(see Appendix C). Nine of these infants died of this complication. The conclusions from this report are as follows:
 - There are no studies to support the use of C1INH outside of those with hereditary angioneurotic edema.
 - The use of C1INH in patients who do not have C1INH deficiency may result in abnormal coagulation parameters with propensity to thrombosis.
 - There are no controlled studies that suggests a benefit of C1INH therapy in conditions other than C1INH deficiency.
 - Any proposed uses outside of C1INH deficiency should be conducted in a controlled manner to monitor for unexpected or unanticipated side effects of C1INH therapy.

Clearly, this is a serious and unanticipated complication of C1INH therapy that could potentially limit its use in patients

with other conditions where complement inhibition would be desirable. This is the case with our proposal. Inhibition of complement activation post-transplant has great potential for prevention of complement-dependent DGF. In addition, there is an important unmet need for new therapeutics in the prevention and treatment of DGF. Despite this, it is important to assess the tolerability and safety of C1INH therapy in this patient population. Although the C1INH dosing proposed in our study is much less than that reported to be associated with TE (50U/kg twice, Days 0 & 1), there is still a possibility that increasing C1INH levels above normal baseline could have deleterious effects and induce coagulation abnormalities. Recent safety data from clinical trials of C1INH for use in C1INH deficiency (Cicardi 2010, 2010 and Zuraw 2010) have not reported TE with one exception of a basilar artery thrombosis in a patient treated for C1INH deficiency (Appendix C). This event was deemed unrelated to C1INH therapy. For that reason, the study will be randomized and patients will be monitored for DVT using the Wells Criteria. In addition, C1INH levels will be obtained at every visit and D-Dimers as well as PT/PTT will be monitored. As previously indicated if significant coagulation abnormalities or TE events are seen in any study patient, the study will be terminated. However, data from our recently completed study of C1INH in prevention of antibody-mediated rejection (NCT01134510) in a randomized placebo controlled study showed no evidence of thrombotic events in any patient treated with Berinert® at 20U/kg x 8 doses given during the first month posttransplant. In addition, recent reports from the FDA (Gandhi et al 2012) suggests that thrombotic events do occur with C1INH therapy, but most cases are associated with the product (Cinryze®). Thus, continued surveillance will be part of this study.

4.6.2.4 Evidence of a Thrombotic Effect of C1INH Administration when Given in Supra-physiologic Dosages to Animals: Data on C1INH transgenic mice show that blood levels as high as 2mg/ml (NL 25 □g/ml) are produced without reported effects (Vinci,2002) (Appendix D). Other investigators have shown that ischemia-reperfusion injury is reduced in animals transgenic for C1INH expression (Vinci, 2002) (Appendix D). Data provided by CSL Berhing (Appendix D) shows that administration of Berinert® up to 200U/kg daily for 14 days had no deleterious effects and did not induce coagulation abnormalities.

CONFIDENTIAL

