4.4 Premature Termination Of Study/Closure Of Center

The sponsor has the right to close this study, and the investigator/sponsor has the right to close a center, at any time, although this should occur only after consultation between involved parties. The Ethics Committee/Institutional Review Board (EC/IRB) must be informed. Should the study/center be closed prematurely, all study materials (except documentation that has to remain stored at site) must be returned to the sponsor. The investigator will retain all other documents until notification given by the sponsor for destruction.

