4.6.2.5 Therapy Stopping Points

As indicated previously, the study will be halted and reevaluated by the DSMB if any patient in the study group develops thrombosis of the allograft, thromboembolic events (TE) or evidence of coagulation abnormalities that would suggest impending TE. In addition, the study will be halted or stopped if any other known or unexpected AEs attributable to C1inhibitor occur. Reassessment of the study goals and complications will be done and discussed with CSL Behring, the DSMB and FDA prior to proceeding.

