1.1.1.6 Primary Safety Endpoints

• Overall incidence of adverse events and serious adverse events and relationship to the study treatment including but not limited to, occurrence of infections, thrombosis of the allograft, vascular thromboses, bleeding, death, vital signs, and abnormal lab values.

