4.6.3.2 Day 0 - Day of Transplantation

- Inclusion/Exclusion criteria (pre-transplant)
- Vital signs (pre- and post-transplant)
- Physical examination (pre- and post-transplant)
- Randomization (pre-transplant)
- Hematology & chemistry profile (pre- and post-transplant)
- PT, PTT and INR (pre- and post-transplant)
- Concomitant medications (pre- and post-transplant)
- ECG (pre-transplant)
- Chest x-ray (pre-transplant)

- Serum Creatinine (pre-and post-transplant, within 4-hours of surgery)
- Clinical Assessment (post-transplant)
- Berinert vs. Placebo infusion (on call to OR)
- C1 inhibitor, C3, C4 levels (prior to dose #1 of C1INH or placebo)
- Campath 1H or Thymoglobulin administration

•

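### After a thromboembolic event, section 4.6.2.3 ends the study while section 4.6.2.5 halts it for DSMB review and allows a restart; the coagulation triggers also differ

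*Combined protocol and SAP*

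**What the plan says.** Section 4.6.2.3, which reviews the evidence on thrombosis in humans, contains a study-level rule: "As previously indicated if significant coagulation abnormalities or TE events are seen in any study patient, the study will be terminated". That sentence mentions neither review nor restart.

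Section 4.6.2.5, headed as the stopping points, gives another: "As indicated previously, the study will be halted and reevaluated by the DSMB if any patient in the study group develops thrombosis". The list goes on from allograft thrombosis to TE events and then to "evidence of coagulation abnormalities that would suggest impending TE". A separate sentence adds that "the study will be halted or stopped if any other known or unexpected AEs attributable to C1inhibitor occur". The section closes by requiring that a reassessment of goals and complications be "discussed with CSL Behring, the DSMB and FDA prior to proceeding".

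Three other places bear on the point:

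- Section 3 requires that the DSMB be told of thromboembolic events and allows it to be convened. It states neither a halt nor a termination, and it refers to a DSMB charter in Appendix E.
- Section 4.4 deals with closing the study in general, "although this should occur only after consultation between involved parties".
- The primary safety endpoints (numbered 1.1.1.6) list "thrombosis of the allograft, vascular thromboses, bleeding, death, vital signs, and abnormal lab values", so allograft thrombosis appears there as an item apart from vascular thromboses.

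**The concern.** One TE event in one patient meets both rules, and the rules prescribe different things. Under 4.6.2.3 the trial is over. Under 4.6.2.5 it pauses and may go on. The site, the sponsor and the DSMB would each hold a protocol that supports either course, and the choice would be made after the event, and possibly its circumstances, were known. A stopping rule is written in advance to avoid exactly that.

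For a coagulation result the position is less clear still, because the two sections may not be triggered by the same finding.

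This matters more here than in most trials. Section 2.1 makes safety the primary objective, and thrombosis is the hazard to which the protocol devotes sections 4.6.2.2 to 4.6.2.4. Which rule governs may also decide whether the planned 70 patients, and the comparison of 35 against 35, are ever reached.

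**Working it through.** **Text comparison.** The protocol states no figure to reproduce. The two rules, trigger by trigger:

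| Trigger | Section 4.6.2.3 | Section 4.6.2.5 |
|---|---|---|
| TE event | Study terminated | Study halted, DSMB re-evaluation, discussion before any continuation |
| Coagulation abnormality | Must be *significant*; study terminated | Must point to an impending TE event; study halted as above |
| Allograft thrombosis | Not named | Named; study halted as above |
| Other AE attributed to C1 inhibitor | Not covered | Study halted or stopped, without saying which |

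1. *TE event.* Same trigger, different action. Termination excludes a restart; a halt followed by re-evaluation does not. Section 4.6.2.5 itself separates halting from stopping, so the words cannot simply be taken as synonyms.
2. *Coagulation abnormality.* Neither trigger is defined in the text available. The numerical INR, PTT and platelet limits in section 4.2.2 concern eligibility, not stopping. A result judged significant but not suggestive of an impending TE event meets the 4.6.2.3 trigger and misses the coagulation trigger in 4.6.2.5.
3. *Allograft thrombosis.* Since 4.6.2.3 does not name it, the protocol does not say whether it counts as a TE event that ends the study.
4. *Precedence.* Each rule opens by claiming to repeat something said before. In the text available (an opening part of the document was not), nothing ahead of 4.6.2.3 sets a rule for halting or ending the study after such events. Section 3 only informs, and may convene, the DSMB. Section 4.4 ranks neither rule.
5. *Who counts.* Section 4.6.2.3 refers to any patient in the study, 4.6.2.5 to any patient in the study group. The synopsis (2.2) uses that term for all 70 patients, while 4.5.7 uses it for a single arm. All 70 is the more natural reading, because 4.5.3 keeps investigators and sponsor blinded.

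**How often a coagulation result could raise the question.** Sections 4.6.3.2 and 4.6.3.3 schedule PT/PTT after the first dose on Day 0 (post-transplant), Day 1 and Day 7. That is 3 × 70 = 210 scheduled panels. This counts opportunities, not expected abnormalities, and assumes every patient has all three.

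**How often a TE event could raise it.** This is an illustration only, because the documents give no TE rate for this population. For an assumed per-patient risk p and independent patients:

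- chance of at least one TE event among n patients = 1 − (1 − p)^n
- expected number enrolled up to the first TE event, capped at 70 = [1 − (1 − p)^70] / p

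At p = 1%: 1 − 0.99^70 = 1 − 0.495 = 0.505, and 0.505 / 0.01 = 50.5.

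| Assumed p | At least one, n = 70 | None, n = 70 | At least one, n = 35 | Expected enrolment if the first event ends the study |
|---|---|---|---|---|
| 0.5% | 0.296 | 0.704 | 0.161 | 59.2 |
| 1% | 0.505 | 0.495 | 0.297 | 50.5 |
| 2% | 0.757 | 0.243 | 0.507 | 37.8 |
| 3% | 0.881 | 0.119 | 0.656 | 29.4 |
| 5% | 0.972 | 0.028 | 0.834 | 19.4 |

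The n = 35 column applies if only one arm counts. The last column assumes that each patient's outcome is known before the next is enrolled. With overlapping follow-up, more patients would already have entered when the first event occurred.

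**The case against.** The best reply is that 4.6.2.5 is the operative rule. It alone carries a heading on stopping, whereas the termination sentence sits inside a review of evidence. Section 4.6.2.5 also presents itself as a restatement, so *terminated* may just be loose drafting. This is a reasonable guess at intent, but the protocol does not say it. The sentence in 4.6.2.3 is itself a directive, and a reader who follows it is following the protocol.

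Second, both rules stop the study at the first TE event, so no patient goes unprotected, and 4.4 already calls for consultation before closure. That stands and limits the point: the dispute is about restart, not about whether to stop. It does not settle the dispute, because consultation before closure does not turn a termination into a pause.

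Third, the coagulation gap is narrower than it looks. Under 7.2.6 a laboratory abnormality that the investigator judges relevant is an AE, and 4.6.2.5 halts or stops the study for other AEs attributed to C1 inhibitor. A significant abnormality attributed to the drug therefore reaches 4.6.2.5 by that route. This is correct. The mismatch remains for abnormalities not attributed to the drug, and even where both sections apply, the stated actions are not the same.

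Finally, the DSMB charter in Appendix E may hold a clear rule. It was not in the text available and could not be checked. A clear charter would help the DSMB but would leave the protocol contradicting itself.

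**Conclusion.** The concern holds. For a TE event in any patient the protocol prescribes both termination and a halt with possible continuation, and it gives neither precedence. For coagulation abnormalities the triggers differ and are undefined, and the actions differ as well. The status of allograft thrombosis under 4.6.2.3 is unstated. These conclusions rest on the wording alone.

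The probabilities show only that the conflict is unlikely to stay theoretical. Over assumed TE risks of 0.5% to 5%, the chance that it arises in 70 patients runs from 30% to 97%. They depend on those assumed rates and on independence between patients, and the contradiction does not depend on them.

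Because the rule concerns the main recognised hazard in a trial whose primary objective is safety, it must be corrected.

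Two lesser matters do not carry this conclusion. The meaning of study group in 4.6.2.5 is a wording question. The clause on other attributable AEs is very broad: read literally, it would include common reactions such as the nausea and headache in 4.6.2.1 whenever they are judged related under 7.2.4. That may be intended and is not a contradiction.

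**What to change.** Reconcile 4.6.2.3 and 4.6.2.5, and bring section 3 and the DSMB charter into line with them. Each trigger (TE event, allograft thrombosis, coagulation abnormality) should have one wording, used everywhere, and lead to one stated action. The text should say whether allograft thrombosis counts as a TE event and whether the study group in 4.6.2.5 means all randomised patients. The references back to earlier text should point to a rule that exists or be removed.

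As a lesser item, the sponsor and DSMB should confirm the intended scope of the clause on other attributable AEs and whether the action is a halt or a stop.

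Which action follows each trigger is for the sponsor and the DSMB to decide; nothing here favours one. The cost is an amendment to the protocol wording and matching charter text, with no new procedures, visits or patients.

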4.6.2.5 Therapy Stopping Points

As indicated previously, the study will be halted and reevaluated by the DSMB if any patient in the study group develops thrombosis of the allograft, thromboembolic events (TE) or evidence of coagulation abnormalities that would suggest impending TE. In addition, the study will be halted or stopped if any other known or unexpected AEs attributable to C1inhibitor occur. Reassessment of the study goals and complications will be done and discussed with CSL Behring, the DSMB and FDA prior to proceeding.

1.1.1.6 Primary Safety Endpoints

• Overall incidence of adverse events and serious adverse events and relationship to the study treatment including but not limited to, occurrence of infections, thrombosis of the allograft, vascular thromboses, bleeding, death, vital signs, and abnormal lab values.

4.6.2.1 Secondary Safety Endpoints

- Chemistry and coagulation parameters
- Patient survival at day 90.
- Graft survival at day 90.
- Rate of acute cellular and antibody mediated rejection episodes at day 90.

4.6.3 Assessment Periods

4.6.3.1 Screening Procedure - Day -30 to Day 0

Prior to screening activities, each patient must be given an opportunity to ask questions and to understand the details of study participation. This consent process must be documented in the patient's source documents and evidenced by the patient signing the informed consent form.

After signing the ICF, each patient will be assigned a patient identifier number that will be used on all subject documentation. Numbers will be assigned in ascending sequential order. This number will also correspond to the patient number entered on study materials.

The Principal Investigator or qualified and assigned Subinvestigator will review the inclusion and exclusion criteria and laboratory test data to confirm eligibility of each subject.

The screening procedures will include the following:

- Informed consent
- Medical history
- Inclusion/Exclusion criteria review
- Vital signs/weight
- Complete physical examination (including DVT exam)
- 12-lead ECG (w/in 6 months)
- Chest X-ray (w/in 6 months)
- Hematology & chemistry profile
- PT, PTT, D-Dimer, Fibrinogen
- Review historical serologies for HIV, HBV, HCV, CMV and EBV
- Pregnancy test (for WOCP)
- Urine output measurement
- Urinalysis
- Concomitant medications
- Pneumococcal vaccine & Neisseria menigitides

4.6.3.2 Day 0 - Day of Transplantation

- Inclusion/Exclusion criteria (pre-transplant)
- Vital signs (pre- and post-transplant)
- Physical examination (pre- and post-transplant)
- Randomization (pre-transplant)
- Hematology & chemistry profile (pre- and post-transplant)
- PT, PTT and INR (pre- and post-transplant)
- Concomitant medications (pre- and post-transplant)
- ECG (pre-transplant)
- Chest x-ray (pre-transplant)

- Serum Creatinine (pre-and post-transplant, within 4-hours of surgery)
- Clinical Assessment (post-transplant)
- Berinert vs. Placebo infusion (on call to OR)
- C1 inhibitor, C3, C4 levels (prior to dose #1 of C1INH or placebo)
- Campath 1H or Thymoglobulin administration

•

4.6.3.3 Day 1-7 Assessments measured daily through day 7 or until discharge

- Berinert vs. Placebo infusion (24hrs post-transplant)
- C1 inhibitor, C3, C4 levels (prior to second dose of C1INH or placebo)
- Urine output between hours of 16-24, 40-48 post transplant
- Concomitant medications
- Serum creatinine measurements daily through Day 7 or until discharge.
- Dialysis assessment
- Vital Signs
- Clinical Assessment
- Calculated Creatinine / Calculated GFR
- Urine output measurement
- Adverse event assessment
- Hematology & chemistry profile
- PT, PTT and INR (day 1 and day 7 only)

•

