SAE medwatch reports WILL NOT be filled out for any prolonged hospital admissions or readmissions that are related to expected complications of the patients' primary disease (ESRD). For example, prolonged admissions for dialysis or readmission for fluid overload as a consequence of ESRD since this this is an expected complication of the patients' disease state and not related to study drug. These events will be adjudicated by the PI. Otherwise, all SAEs medwatch reports will be submitted to the IRB, study sponsor and FDA.

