7.2.6 Adverse Event (AE) Documentation

All AEs occurring after the subject has signed the informed consent must be fully recorded in the subject's case record form.

Documentation must be supported by an entry in the subject's file. A laboratory test abnormality considered clinically relevant, e.g., causing the subject to withdraw from the study, requiring treatment or causing apparent clinical manifestations, or judged relevant by the investigator, should be reported as an AE. Each event should be described in detail along with start and stop dates, severity, relationship to investigational product, action taken and outcome.

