Appendix A

Study visit										
	Screening	Transplant Day 0 (Infusion #1 C1INH vs Placebo)	Day 1±6 hrs (Infusion #2 C1INH vs Placebo)	Day 2±6 hrs	Day 3±6 hrs	Day 4±6 hrs	Day 5±1 days	Day 6±2 days	Day 7±3 days *	Day 14 ±3 days
Informed Consent	Х									
Inclusion/exclusi on criteria review	^ X									
Medical History	X									
Complete Physical Exam (Including DVT Exam) (1)	X	X	X	X	Х	X	X	X	x	
Vital										
signs/weight	Χ	Х	X	Х	Х	Х	Х	Х	Х	Х
12-lead ECG (w/in 6M)	Х									
Chest X-ray (w/in 6M)	Х									
Safety laboratory tests (CBC, CMP)	X	Х	Х	Х	х	Х	Х	Х	Х	Х
PT, PTT, D. Dimer, Fibrinogen	Х	Х	Х						Х	
Review Historical Serologies for HIV, HBV, HCV, CMV and EBV	X									
Pregnancy test (for WOCP)	X									
Urinalysis	Х									Х
Urine Output		v	v	V	V	Х	V	Х		
Measurement Estimated GFR (using MRDR or Cockroft & Gault		X	X	X	X		X		X	
equation)			Х	Х	Х	Х	Χ	Х	Х	Χ

OOMITEDENTIA		OTTIVII (DCI	ernerco, in	1 Deady	±11 1(±0	11101 11	amopia			
Allograft biopsy		Х								
Dialysis	1		+	+						
Assessment	ı	X	X	Х	Х	Х	Х	Χ	х	Х
Assessment for					1					
DVT (Using Wells	ı									
Criteria Score)	ı									
(2)		X	Х						Х	
Pneumococcal	ı									
Vaccine &	ı									
Neiserria	ı									
Menigitides	Х				 				 	 
Berinert® vs	ı									
Placebo Infusion	ı									
_		X	Х		 	 	 	  '	 	1
C3, C4 Levels		Χ	Х		 	 		'	Х	
C1 Inhibitor				T						
Level (Prior to	1									
each infusion)		Χ	X						Х	
Campath or	1									
Thymoglobulin	ı									
administration	 	X			 		 		 	
Concomitant	ı									
medications	Х	X	Х	Х	X	Х	Х	Χ	Х	Х
Adverse Event	ı									
Monitoring	ı		X	Х	X	Х	Х	Х	Х	Х
Acute Rejection										
Assessment	1									

- (1) DVT exam will be done on day 0 and day1 (days Berinert vs.Placebo are given)
- (2) For scores indicating high risk for DVT, patient will have Doppler ultrasound.

*Day 4-7 assessments should be performed daily until the patient is discharged.

**If patient is discharged prior to day 7, day 7 lab assessments should be performed.

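### Week-1 safety assessments stop at discharge and only the day 7 labs are explicitly restored, so transient vital-sign and laboratory findings may be under-detected in whichever arm goes home earlier

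*Combined protocol and SAP*

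**What the plan says.** Section 4.6.3.3 lists the AE assessment, vital signs, clinical assessment and hematology/chemistry under the heading "Assessments measured daily through day 7 or until discharge". The Appendix A footnotes agree: "Day 4-7 assessments should be performed daily until the patient is discharged". A second footnote covers early discharge, but names laboratory work only: "If patient is discharged prior to day 7, day 7 lab assessments should be performed". The next visits, common to all patients, are at days 14 and 28 (section 4.6.3.4) and days 60 and 90 (section 4.6.3.5). Each includes an AE assessment, vital signs and labs.

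The primary safety endpoint is "Overall incidence of adverse events and serious adverse events and relationship to the study treatment". Its listed components include "bleeding, death, vital signs, and abnormal lab values". Section 7.2.6 sets no stop at discharge: "All AEs occurring after the subject has signed the informed consent must be fully recorded in the subject's case record form". Section 7.3 likewise carries SAE reporting through follow-up.

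Section 6.1 (statistical and analytical plans) is a heading without text. The synopsis promises descriptive and comparative statistics and says nothing about unequal observation.

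**The concern.** Discharge happens after randomisation and plausibly depends on graft function. Section 7.2.2 gives "prolonged admissions for dialysis or readmission for fluid overload as a consequence of ESRD" as an expected consequence of the underlying disease. Graft function is what C1INH is meant to improve. If it does, more C1INH patients leave before day 7 and have fewer scheduled looks. Blinding does not prevent this, because discharge can follow graft function without anyone knowing the arm.

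A patient can report symptoms at day 14. A brief laboratory or vital-sign abnormality that nobody measured cannot be recovered. The unobserved days also come soon after dosing: the second dose is at 24 hours, and section 4.1.1 gives a half-life of about 2.5 to 3.8 days. Safety is the primary objective, so a comparison of crude incidence could make the arm discharged earlier look somewhat safer than it is.

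**Working it through.** **Inputs from the protocol.** DGF of 50% on placebo and 25% on C1INH (section 6.2, which also tabulates 20% and 30%); 35 patients per arm (section 4.5.7); common visits at days 14, 28, 60 and 90. The protocol gives no figure for AE ascertainment. Its nearest figure, 66 per group for 50% versus 25% (two-sided 0.05, 80% power, continuity-corrected), reproduces: the uncorrected n is 57.7, and (57.7/4) × [1 + √(1 + 4/(57.7 × 0.25))]² = 65.4, rounded up to 66. Only the DGF rates are used below.

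**Assumptions not in the protocol.** Patients with DGF stay through day 7. Others leave on day d = 3, 4 or 5. Each contact has the same chance h of a recordable finding in both arms, with h from 2% to 20%. Anything between contacts is lost, which is the worst case.

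**Step 1: assessed days in week 1.** Mean = p × 7 + (1 − p) × d, where p is the DGF rate.

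| d | Placebo (p = 0.50) | C1INH (p = 0.25) | Ratio |
|---|---|---|---|
| 3 | 5.00 | 4.00 | 0.80 |
| 4 | 5.50 | 4.75 | 0.86 |
| 5 | 6.00 | 5.50 | 0.92 |

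That is 8 to 20% fewer assessed days on C1INH.

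**Step 2: any finding in week 1.** Incidence = p[1 − (1 − h)^7] + (1 − p)[1 − (1 − h)^d]. With h = 10% and d = 4, a neutral drug shows 43.3% versus 38.8%. In general the gap is (0.50 − 0.25) × [(1 − h)^k − (1 − h)^m], where k is the number of contacts for a patient discharged early and m the number for one who stays. With k = d and m = 7 it runs from 0.9 to 7.6 points.

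**Step 3: add the day 7 labs.** With k = d + 1, the week-1 gap falls to 0.4 to 5.0 points.

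**Step 4: through day 90.** Four common visits follow, so m = 11.
- With the day 7 contact (labs), k = d + 5. The largest gap on this grid is at d = 3, h = 10%: 0.25 × (0.9^8 − 0.9^11) = 0.25 × (0.4305 − 0.3138) = 2.9 points, or 0.029 × 35 = 1.0 patient. The range is 0.4 to 2.9 points.
- Without a day 7 contact (vital signs, if the footnote is read as labs only), k = d + 4. The largest gap is 0.25 × (0.9^7 − 0.9^11) = 0.25 × (0.4783 − 0.3138) = 4.1 points, or 1.4 patients in 35. The smallest, at d = 5 and h = 2%, is 0.25 × (0.98^9 − 0.98^11) = 0.8 points.

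**Step 5: sensitivity.** With DGF of 50% versus 35%, the day 90 gap with the day 7 contact is 0.2 to 1.7 points. With equal DGF and stay it is zero. If C1INH lengthened stay, the sign would reverse.

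**Step 6: would an AE rate per assessed day help?** Suppose findings are front-loaded, with assumed daily chances of 30, 20, 10 and then 5%, and d = 4. The week-1 gap for a neutral drug is then 0.25 × (58.9% − 52.1%) = 1.7 points. Expected findings are 0.80 for a patient who stays and 0.65 for one who leaves. Per assessed day this gives (0.5 × 0.80 + 0.5 × 0.65)/5.50 = 0.132 on placebo and (0.25 × 0.80 + 0.75 × 0.65)/4.75 = 0.145 on C1INH. The neutral drug now looks about 10% worse, so the rate swaps one bias for the opposite one.

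**The case against.** A reader might infer that the schedule is built to favour C1INH. The documents do not support that. Both blinded arms follow the same schedule, and a difference arises only if C1INH changes length of stay.

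A reader might also take the week-1 gap of up to 7.6 points as the bias in the primary safety endpoint. That fails too. The endpoint is not limited to week 1, AEs and SAEs stay recordable after discharge, and four later visits are common to both arms. Section 7.2.6 treats a laboratory abnormality as an AE only when it is clinically relevant, so many silent transient values would not count. Section 4.6.3.3 fixes PT, PTT and INR at days 1 and 7, so the coagulation tests have common time points. No length of stay, discharge day or AE rate is given anywhere. With 35 per arm and incidence near 40%, the 95% half-width for a difference is about 1.96 × √(2 × 0.4 × 0.6/35) = 23 points, far wider than any gap computed here.

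All of this stands, and it makes the point a small one. A further argument is that the Day 7 column of Appendix A already includes vital signs and AE monitoring, with a window of ±3 days. This helps only in part. The footnote names labs alone for patients who have left, and a day 7 entry completed on day 4, before discharge, leaves the following days unobserved.

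**Conclusion.** The point holds as a possible difference in ascertainment of transient vital-sign and laboratory findings between discharge and day 7 or day 14. It does not show a built-in advantage for C1INH, and it does not show that any real harm would be masked: the calculations model only a neutral drug.

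The size is modest. Through day 90 the worst case is 0.4 to 2.9 points for findings covered by the day 7 contact. It is 0.8 to 4.1 points for those that are not. These figures rest on assumed discharge days, an assumed constant chance per contact, and the protocol's hypothesised DGF rates. Symptomatic AEs, SAEs and PT/PTT/INR are largely unaffected. This is a cheap improvement of minor severity, best made before data are collected because missed measurements cannot be recovered afterwards.

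**What to change.** 1. Extend the early-discharge footnote in Appendix A. The day 7 contact already required for labs should also cover the AE query, vital signs and the other safety assessments in the Day 7 column, including the Wells score.
2. State in section 6.1 that laboratory and vital-sign abnormalities are compared between arms at time points scheduled for every patient (days 0, 1, 7, 14, 28, 60 and 90). All other inpatient values are still reported descriptively by arm.
3. Do not add an AE rate per assessed day. Its denominator is set after randomisation and misleads when events are front-loaded.

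The cost is one footnote sentence, one analysis sentence and a few minutes per patient discharged early. Values from days 2 to 6 become descriptive only, so they should still be displayed in full.
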